6.2.2. Day 1 Assessments

Day 1 assessments, including study drug administration, will be done at the study center. The following will be performed and documented prior to dosing:

• Updates to medical history

- Weight
- Symptom-driven physical examination
- Vital signs (blood pressure, heart rate, respiratory rate, and temperature)
- PGA
- CLASI
- Detailed target lesion assessment (see Section 6.9.2.3 for details)
- Photographs of areas with skin involvement (identifying subject features should be obscured, as much as possible)
- Detailed mucous membrane assessment (see Section 6.9.2.4 for details)
- Subject questionnaires:
 - Subject's global assessment of CLE disease activity
 - Subject assessment of autoimmune disease-related dry eyes/mouth
 - Subject assessment of autoimmune disease-related body pain
 - Subject assessment of autoimmune disease-related joint pain/stiffness
 - Subject assessment of autoimmune disease-related fatigue
 - Subject assessment of CLE on sexual activity
 - SF-36
 - DLQI
 - TSQM
- Obtain blood samples for:
 - Clinical Laboratory Tests (hematology, serum chemistry, and coagulation)
 - Fasting lipids (overnight fast [no food or drinks, except water] of at least 8 hours required prior to blood sample collection)
 - CRP and ESR
 - Quantitative Serum Immunoglobulin Test
 - Autoantibody Panel and Complement Levels

- Biomarker Samples (predose)
 - Whole Blood, Cytochex
 - o Whole Blood, Heparin
 - Serum and plasma biomarker samples
 - o vfPBMC sample
 - o PAXgene RNA sample

- Obtain urine sample for:
 - Urinalysis
 - Urine pregnancy test (for females of childbearing potential)
 - Urine protein to creatinine ratio

- After the subject's eligibility for the study has been confirmed, the subject will be randomized to 1 of 3 arms
- Study drug dispensation
- Review and record all adverse events and concomitant medications

6.3. Randomization

Upon qualification for the study, subjects will be randomized in a 2:2:1 ratio using a computerized IWRS system on the Day 1 visit.

For each subject at each dispensation visit, the clinic will contact the IWRS system for the appropriate kit number to be dispensed. The kit will contain the relevant study drug for the period until the next dispensation visit.

Refer to Sections 3.3 and Section 6.1 for additional details.

6.4. Week 2 through Week 24 (Study Dosing Period)

The following assessments will be completed as specified in the Study Procedures Table (Appendix 2).

• Weight

- Symptom-driven physical examination
- Vital signs (blood pressure, heart rate, respiratory rate, and temperature)
- PGA
- CLASI
- Detailed target lesion assessment (see Section 6.9.2.3 for details)
- Photographs of areas with skin involvement (identifying subject features should be obscured, as much as possible)
- Detailed mucous membrane assessment (Weeks 2, 12, 14, and 24; see Section 6.9.2.4 for details)
- Subject questionnaires:
 - Subject's global assessment of CLE disease activity
 - Subject assessment of autoimmune disease-related dry eyes/mouth
 - Subject assessment of autoimmune disease-related body pain
 - Subject assessment of autoimmune disease-related joint pain/stiffness
 - Subject assessment of autoimmune disease-related fatigue
 - Subject assessment of CLE on sexual activity
 - SF-36
 - DLOI
 - TSQM
- Standard 12-lead ECG (Week 24 only)
- HCV monitoring (Weeks 12 and 24; if applicable)
- Obtain blood samples for:
 - Clinical Laboratory Tests (hematology, serum chemistry, and coagulation)
 - Fasting Lipids (Weeks 12 and 24; overnight fast [no food or drinks, except water] of at least 8 hours required prior to blood sample collection)
 - CRP and ESR
 - Quantitative Serum Immunoglobulin Test (Weeks 8 and 20)
 - Autoantibody Panel and Complement Levels (Weeks 12 and 24)

- Biomarker Samples (Weeks 2, 4, 12, and 24)
 - Whole Blood, Cytochex
 - o Whole Blood, Heparin
 - o Serum and plasma biomarker samples
 - vfPBMC sample
 - o PAXgene RNA sample
- Pharmacokinetic Samples (Week 2 [at least 30 minutes and up to 3 hours after dosing], Week 4 [anytime], Week 12 [within 2 hours prior to study drug administration], and Week 24 [within 2 hours prior to study drug administration])
- Obtain urine sample for:
 - Urinalysis
 - Urine pregnancy test (for females of childbearing potential)
 - Urine protein to creatinine ratio
- Re-randomization 1:1 upon completion of Week 12 assessments (subjects on placebo only, will be performed in a double-blind fashion via IWRS)
- Study drug dispensation (not applicable at Weeks 2 and 14 and not applicable at Week 24 for subjects who do not enter the 24-week extension period)
- Study drug accountability
- Review and record all adverse events and concomitant medications

6.5. Week 30 through Week 48 (24-week Extension Period)

The following assessments will be completed at each visit or as specified. All assessments are summarized in the Study Procedures Table (Appendix 2).

- Weight
- Symptom-driven physical examination
- Vital signs (blood pressure, heart rate, respiratory rate, and temperature)
- PGA

- CLASI
- Detailed target lesion assessment (see Section 6.9.2.3 for details)
- Photographs of areas with skin involvement (identifying subject features should be obscured, as much as possible)
- Detailed mucous membrane assessment (Weeks 36 and 48; see Section 6.9.2.4 for details)
- Subject questionnaires:
 - Subject's global assessment of CLE disease activity
 - Subject assessment of autoimmune disease-related dry eyes/mouth
 - Subject assessment of autoimmune disease-related body pain
 - Subject assessment of autoimmune disease-related joint pain/stiffness
 - Subject assessment of autoimmune disease-related fatigue
 - Subject assessment of CLE on sexual activity
 - SF-36
 - DLQI
 - TSQM
- Standard 12-lead ECG (Weeks 36 and 48)
- HCV monitoring (Weeks 36 and 48; if applicable)
- Obtain blood samples for:
 - Clinical Laboratory Tests (hematology, serum chemistry, and coagulation)
 - Fasting Lipids (Week 42 only; overnight fast [no food or drinks, except water] of at least 8 hours required prior to blood sample collection)
 - CRP and ESR
 - Quantitative Serum Immunoglobulin Test (Week 42 only)
 - Autoantibody Panel and Complement Levels (Week 42 only)
 - Biomarker Samples (Week 48 only)
 - Serum and plasma biomarker samples
 - o PAXgene RNA sample
- Obtain urine sample for:
 - Urinalysis

- Urine pregnancy test (for females of childbearing potential). When visits are greater than 4 weeks apart, women should continue to have urine pregnancy tests every 4 weeks using at home pregnancy test kits that will be provided to them. The site will call the subject every 4 weeks to obtain results of these pregnancy tests and will record the information in the source documents and eCRF. If any urine pregnancy test is positive, study drug should be immediately interrupted and the subject should return to the study center for a serum pregnancy test
- Urine protein to creatinine ratio
- Study drug dispensation (not applicable at Week 48)
- Study drug accountability
- Review and record all adverse events and concomitant medications

6.6. Follow-up Assessments

A FU visit will be conducted 4 weeks after the last dose of study drug. Subjects who discontinue study drug \geq 4 weeks prior to their last visit will not be asked to return for a FU visit.

- Weight
- Symptom-driven physical examination
- Vital signs (blood pressure, heart rate, respiratory rate, and temperature)
- PGA
- CLASI
- Detailed target lesion assessment (see Section 6.9.2.3 for details)
- Photographs of areas with skin involvement (identifying subject features should be obscured, as much as possible)
- Subject questionnaires:
 - Subject's global assessment of CLE disease activity
 - Subject assessment of autoimmune disease-related dry eyes/mouth
 - Subject assessment of autoimmune disease-related body pain
 - Subject assessment of autoimmune disease-related joint pain/stiffness
 - Subject assessment of autoimmune disease-related fatigue
 - Subject assessment of CLE on sexual activity

- SF-36
- DLQI
- Obtain blood samples for:
 - Clinical Laboratory Tests (hematology, serum chemistry, and coagulation)
 - Complement Levels
 - Biomarker Samples
 - o Serum and plasma biomarker samples
 - o PAXgene RNA sample
- Obtain urine sample for:
 - Urinalysis
 - Urine pregnancy test (for females of childbearing potential)
 - Urine protein to creatinine ratio
- Review and record all adverse events and concomitant medications

6.7. Early Termination Assessments

Subjects who discontinue the study prior to Week 24 (or prior to Week 48 for subjects entering the 24-week extension period) will return to the study center for the ET visit.

- Weight
- Symptom-driven physical examination
- Vital signs (blood pressure, heart rate, respiratory rate, and temperature)
- PGA
- CLASI
- Detailed target lesion assessment (see Section 6.9.2.3 for details)
- Photographs of areas with skin involvement (identifying subject features should be obscured, as much as possible)
- Subject questionnaires:
 - Subject's global assessment of CLE disease activity

- Subject assessment of autoimmune disease-related dry eyes/mouth
- Subject assessment of autoimmune disease-related body pain
- Subject assessment of autoimmune disease-related joint pain/stiffness
- Subject assessment of autoimmune disease-related fatigue
- Subject assessment of CLE on sexual activity
- SF-36
- DLQI
- TSQM
- Standard 12-lead ECG (if not completed within the prior 12 weeks)
- HCV monitoring (if applicable, if not completed within the prior 12 weeks)
- Obtain blood samples for:
 - Clinical Laboratory Tests (hematology, serum chemistry, and coagulation)
 - CRP and ESR
 - Complement Levels
 - Biomarker Samples
 - Whole Blood, Cytochex
 - Whole Blood, Heparin
 - Serum and plasma biomarker samples
 - o vfPBMC sample
 - PAXgene RNA sample
- Obtain urine sample for:
 - Urinalysis
 - Urine pregnancy test (for females of childbearing potential)
 - Urine protein to creatinine ratio
- Study drug accountability
- Review and record all adverse events and concomitant medications

6.8. Unscheduled Visit Assessments

A subject should attend an unscheduled visit if requested by the sponsor or the investigator. The assessments performed are at the investigator's discretion.

6.9. Study Assessments

6.9.1. Priority of Assessments

Subject-reported outcomes are recommended to be completed before any other study procedures. Invasive study procedures such as blood draws and biopsies should be done at the end of a study visit, as much as possible. Investigator questionnaires/assessments should be performed prior to reviewing subject-reported outcomes for that visit, as much as possible.

6.9.2. Efficacy

Efficacy assessments will be performed at the time points indicated in the Study Procedures Table (Appendix 2).

6.9.2.1. Cutaneous Lupus Erythematosus Disease Area and Severity Index (CLASI)

The CLASI is assessed using a one-page tool which lists each part of the body separately and results in separate scores for skin damage and disease activity.

6.9.2.2. Physician's Global Assessments of CLE Disease Activity

The Physician's Global Assessment of CLE Disease Activity will be recorded on a 0-100 mm visual analogue scale (VAS; Appendix 7), with 0 indicating "no CLE disease activity" and 100 indicating "maximum CLE disease activity". The evaluating physician and the subject should complete the global assessments independently of each other.

6.9.2.3. Detailed Target Lesion Assessments

The investigator will identify a highly clinically active lesion on Day 1. The lesion will be measured and assessed for edema (0 = absent, 1 = slight, just palpable, 2 = visible and palpable). The area that was assessed will be recorded in the source documents.

6.9.2.4. Detailed Mucous Membrane Assessments

Mucous membranes will be assessed for lesions at the buccal mucosa, the hard and soft palates, and the nasal mucosal areas for erythema, keratosis, and erosions and scored as indicated below.

Area of Lesion Assessment	Erythema	Keratosis	Erosions
Buccal Mucosa	0 = absent 1 = present	0 = absent 1 = present	0 = absent 1 = erosion 2 = ulceration
Hard and Soft Palates	0 = absent 1 = present	0 = absent 1 = present	0 = absent 1 = erosion 2 = ulceration
Nasal Mucosal Areas	0 = absent 1 = present	0 = absent 1 = present	0 = absent 1 = erosion 2 = ulceration

6.9.2.5. Subject's Global Assessment of CLE Disease Activity

The Subject's Global Assessment of CLE Disease Activity will be recorded on a 0-100 mm VAS, with 0 indicating "I have no CLE" and 100 indicating "I have the worst CLE."

6.9.2.6. Subject Assessment of Autoimmune Disease-Related Dry Eyes/Mouth

The Subject Assessment of Autoimmune Disease-Related Dry Eyes/Mouth will be recorded on a 0-100 mm VAS (Appendix 8), with 0 indicating "I have no dry eye/mouth due to my autoimmune condition" and 100 indicating "I have the worst dry eye/mouth due to my autoimmune."

6.9.2.7. Subject Assessment of Autoimmune Disease-Related Body Pain

The Subject Assessment of Autoimmune Disease-Related Body Pain will be recorded on a 0-100 mm VAS (Appendix 8), with 0 indicating "I have no body pain due to my autoimmune condition" and 100 indicating "I have the worst body pain due to my autoimmune condition."

6.9.2.8. Subject Assessment of Autoimmune Disease-Related Join Pain/Stiffness

The Subject Assessment of Autoimmune Disease-Related Joint Pain/Stiffness will be recorded on a 0-100 mm VAS (Appendix 8), with 0 indicating "I have no joint pain/stiffness due to my autoimmune condition" and 100 indicating "I have the worst joint pain/stiffness due to my autoimmune condition."

6.9.2.9. Subject Assessment of Autoimmune Disease-Related Fatigue

The Subject Assessment of Autoimmune Disease-Related Fatigue will be recorded on a 0-100 mm VAS (Appendix 8), with 0 indicating "I have no fatigue due to my autoimmune condition" and 100 indicating "I have the worst fatigue due to my autoimmune condition."

6.9.2.10. Subject Assessment of CLE on Sexual Activity

The Subject Assessment of CLE on Sexual Activity will be recorded on a 0-100 mm VAS (Appendix 8), with 0 indicating "my CLE does not affect my sexual activity" and 100 indicating "my CLE completely stops my sexual activity."

6.9.2.11. 36-Item Short Form Healthy Survey

The SF-36 is a health related quality of life instrument consisting of 36 questions belonging to 8 domains in 2 components and covers a 4-week recall period:

- Physical well-being, 4 domains: physical functioning (10 items), role physical (4 items), bodily pain (2 items), and general health perceptions (5 items)
- Mental well-being, 4 domains: vitality (4 items), social functioning (2 items), role emotional (3 items), and mental health (5 items).

The remaining item (health transition) is not part of the above domains but is kept separately. These scales will be rescaled from 0 to 100 (converting the lowest possible score to 0 and the highest possible score to 100), with higher scores indicating a better quality of life. The SF-36 is not disease specific and has been validated in numerous health states.

6.9.2.12. Dermatology Quality of Life Index (DLQI)

The DLQI is a 10-question questionnaire used to measure the impact of skin disease on the quality of life of an affected person. Subjects will assess the impact of skin disease based on the previous week. Dermatology Quality of Life Index topics include symptoms and feelings, daily activities, leisure, work and school, personal relationships, and treatment. Each question is scored from 0 to 3 (0 = not at all, not relevant, or question unanswered; 1 = a little, 2 = a lot, 3 = very much).

6.9.2.13. Treatment Satisfaction Questionnaire for Medication

The TSQM is a composite measure based on the subject's rating of medication effectiveness, side effects, and convenience.

At Day 1, this questionnaire will be used to assess prior medications used to treat the subject's CLE. At all other time points, the TSQM will be used to assess the subject's opinion of the study drugs. Site staff should remind the subject of which CLE drugs they should be evaluating at each visit.

6.9.3. Safety

Safety will be assessed via AEs, concomitant medications, physical examinations (complete and symptom-driven), vital signs, ECGs, and clinical laboratory results.

6.9.4. Clinical Laboratory Evaluations

The hematology, serum chemistry, and coagulation laboratory analyses will be performed at a central laboratory. Reference ranges will be supplied by the central laboratory and will be used by the investigator to assess the laboratory data for clinical significance and pathological changes.

Blood samples will be collected by venipuncture CCI in the arm at the time points indicated in the Study Procedures Table (Appendix 2). In addition, urine samples for the clinical laboratory assessments will be collected. An overnight fast (no food or drinks, except water) of at least 8 hours will be required prior to collection of blood samples for lipid testing.

• Refer to Appendix 6 for table of clinical laboratory tests.

Laboratory values outside the normal range will be flagged and clinical relevance will be assessed by the investigator (refer to Section 7.5). More frequent sampling as well as additional tests may be performed as deemed necessary by the investigator.

Note that in the case where clinically significant laboratory test results are a potential reason for discontinuation from the study drug and/or withdrawal from the study, retesting of the affected parameter(s) should be prompt (within 3 to 7 days) (see Section 3.5 for additional information).

The details of sample handling and shipment instructions will be provided in a separate laboratory manual.

6.9.5. Vital Signs

Vital signs will be measured at the time points indicated in the Study Procedures Table (Appendix 2).

Vital signs should be taken after the subject has been resting in the seated or supine position for at least 5 minutes and will include pulse rate, respiratory rate, systolic and diastolic blood pressure, and temperature.

6.9.6. Physical Examination

A physical examination should be performed at the time points indicated in the Study Procedures Table (Appendix 2). Any changes from screening will be recorded. Weight will be measured at all visits. Height will be measured at screening only. Subjects should be instructed to remove shoes prior to measurement of height.

At screening, a complete physical examination will be performed. A complete physical examination will include source documentation of general appearance and the following body systems: head, neck, and thyroid; eyes, ears, nose, throat, mouth and tongue; chest (excluding breasts); respiratory; cardiovascular; lymph nodes; abdomen; skin, hair, nails; musculoskeletal; and neurological. Symptom-driven physical examinations will be performed at all other visits based on reported signs and symptoms.

6.9.7. Other Safety Assessments

6.9.7.1. 12-lead Electrocardiogram

A resting 12-lead ECG will be performed at the time points indicated in the Study Procedures Table (Appendix 2).

The ECG should be obtained after the subject has been resting in the supine position for at least 5 minutes and will include heart rate (HR), inter-beat (RR), QRS, uncorrected QT, morphology, and rhythm analysis. QT interval corrected for HR according to Fridericia (QTcF) will be derived during the statistical analysis. Electrocardiograms will be interpreted by the investigator (or qualified designee) for clinical significance and results will be entered into the eCRF.

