Safety pharmacology studies showed no clinically-relevant effects on the respiratory, and CNS systems after single oral doses up to 300 mg/kg. Cardiovascular effects in telemetered cynomolgus monkeys at ≥ 20 mg/kg included prolonged QTc interval from 5 through 25 hours postdose, slightly higher systolic, diastolic, and mean arterial pressure with lower heart rate through 6 hours postdose, and higher heart rate from 9 through 25 hours postdose. While differences in QTc interval were generally small, the changes were of sufficient magnitude to be considered biologically relevant. There were no inhibitory effects on the hERG potassium current when GS-9876 was tested up to a free drug concentration of 30 μ M, which is approximately 207-fold above the observed steady state C_{max} at a 30 mg once daily dose. Further, no cardiovascular effects were observed in telemetered cynomolgus monkeys administered GS-9876 for 39 weeks at doses up to 15 mg/kg/day. The potential for GS-9876 to prolong the QTc interval was assessed with intensive time-matched electrocardiogram (ECG) monitoring in Gilead clinical studies GS-US-379-1372 and GS-US-379-1900, and no clinically significant changes in time-matched QTc intervals or in serial vital sign measurements were observed.

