7.5. Electrocardiogram Results

A shift table of the investigators' assessment of ECG results at each visit compared with baseline values will be presented by treatment group using the following categories: normal; abnormal, not clinically significant; abnormal, clinically significant; or missing. The number and

percentage of subjects in each cross-classification group of the shift table will be presented. Subjects with a missing value at baseline or postbaseline will not be included in the denominator for percentage calculation. No formal statistical testing is planned.

A by-subject listing for ECG assessment results will be provided by subject ID number and visit in chronological order.

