7.7. Changes From Protocol-Specified Safety Analyses

There are no deviations from the protocol-specified safety analyses.

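### The protocol commits to deriving QTcF in the analysis, but the SAP plans no numerical QT or QTcF analysis and does not record the omission

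*Protocol*

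**What the plan says.** Protocol 6.9.7.1 says that each ECG "will include heart rate (HR), inter-beat (RR), QRS, uncorrected QT, morphology, and rhythm analysis", and then that "QT interval corrected for HR according to Fridericia (QTcF) will be derived during the statistical analysis". It adds: "Electrocardiograms will be interpreted by the investigator (or qualified designee) for clinical significance". The protocol synopsis lists ECGs among the safety assessments and gives a general rule that continuous safety data are summarised by arm with eight statistics (n, mean, SD, median, quartiles, minimum, maximum).

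SAP 7.5 contains two outputs. One is a shift table in which the investigators' "assessment of ECG results at each visit compared with baseline values will be presented by treatment group using the following categories": normal, abnormal but not clinically significant, abnormal and clinically significant, or missing. The other is a listing: "A by-subject listing for ECG assessment results will be provided by subject ID number and visit in chronological order". QTcF is defined in the SAP's list of abbreviations and appears in no analysis section. SAP 7.7 states: "There are no deviations from the protocol-specified safety analyses".

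**The concern.** The protocol assigns a specific derivation to the statistical analysis, and the SAP neither carries it out nor says that it has been dropped. A programmer working from the SAP alone would produce no QTcF variable.

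This matters most for GS-9876. Protocol 1.3.2.1 reports a longer QTc interval in monkeys at 20 mg/kg and above. It calls the differences generally small, but adds that "the changes were of sufficient magnitude to be considered biologically relevant". The trial doses subjects for up to 48 weeks, whereas the multiple-dose healthy-volunteer study described in Protocol 1.4.2 dosed for 7 days. A categorical reading shows neither the size of a mean change in QTcF nor how many subjects exceed a given value or increase. No efficacy result is affected.

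**Working it through.** There is no plan figure to reproduce on this point. The check is a comparison of text, a count of scheduled ECGs, and a precision calculation for the proposed summary.

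**Step 1. Text side by side.**
- Protocol 6.9.7.1: HR, RR, QRS and uncorrected QT are part of each ECG, and QTcF is to be derived in the analysis.
- Protocol synopsis: continuous safety data get an eight-number summary by arm.
- Protocol 8.6: laboratory tests, physical examinations, vital signs and adverse events are named. ECGs are not.
- SAP 7.5: a category shift table and a listing. It has no derivation, interval summary, change from baseline or threshold table, and no redaction mark that could hide one.
- SAP 7.7: no deviations.

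The SAP is therefore consistent with Protocol 8.6 taken alone, but not with Protocol 6.9.7.1 or with the synopsis rule.

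**Step 2. Which ECGs exist.** Protocol Appendix 2 schedules ECGs at screening and Weeks 24, 36 and 48, and at early termination if none was done in the prior 12 weeks.
- Scheduled on-treatment ECGs up to Week 12: 0.
- Scheduled on-treatment ECGs after Week 12: 3.

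Placebo subjects are re-randomised to active drug at Week 12. At Weeks 24, 36 and 48 they will have had 24 − 12 = 12, 36 − 12 = 24 and 48 − 12 = 36 weeks of active drug. No scheduled ECG is taken on placebo. Because none is scheduled between screening and Week 24, the screening ECG serves as baseline whether the clock starts at Day 1 or at the first active dose.

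**Step 3. Precision of a within-group mean change.**
- Formula: 90% half-width = t(0.95, n − 1) × SD / √n.
- n = 20 is the planned size of each active arm. n = 18 applies the sample-size section's 10% drop-out (20 × 0.9).
- The SD of change in QTcF is not in the documents. A range of 10 to 20 ms is assumed.

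| SD (ms) | n = 20, t = 1.729 | n = 18, t = 1.740 |
|---|---|---|
| 10 | 1.729 × 10 / √20 = 3.9 | 1.740 × 10 / √18 = 4.1 |
| 15 | 1.729 × 15 / √20 = 5.8 | 1.740 × 15 / √18 = 6.2 |
| 20 | 1.729 × 20 / √20 = 7.7 | 1.740 × 20 / √18 = 8.2 |

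The range is about 4 to 8 ms. The 10% drop-out was assumed for the Week 12 endpoint and the extension is optional, so n may be smaller, and the interval wider, at Weeks 36 and 48.

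**The case against.** The strongest reply is that SAP 7.7 speaks of protocol-specified safety analyses, and Protocol 8.6, the section that specifies them, contains no ECG analysis. Section 6.9.7.1 describes an assessment and promises a derived variable, not tables of change or outliers. This stands in part. SAP 7.7 can be defended against 8.6 alone, and the outlier categories proposed below are not a protocol requirement. It does not answer the plain commitment to derive QTcF in the analysis, or the synopsis rule, which would apply to QTcF once derived.

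A second reply is that the gain is modest. A half-width of 4 to 8 ms will not reliably show a shift of a few milliseconds, and without a placebo comparison drug effect cannot be separated from drift. Both points are correct. They limit how the result can be read, but a within-group summary and a count of individual increases would still be information that the plan does not now produce.

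A third reply is that the intervals may not be in the database. Protocol 6.9.7.1 says that results go into the eCRF without saying whether that means the intervals or only the interpretation. This cannot be settled from the documents.

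Two stronger readings are tempting, and the documents do not support them. A reader might infer that the QTc signal goes unexamined. Protocol 1.3.2.1 reports intensive time-matched ECG monitoring in two clinical studies with no clinically significant QTc change. It also reports no hERG inhibition up to 30 µM (about 207-fold above the observed steady-state Cmax at 30 mg) and no cardiovascular effects in monkeys over 39 weeks at up to 15 mg/kg/day. In this trial the investigator still reads each ECG. A reader might also infer that these are the first lupus patients to receive GS-9876, but Protocol 1.3.3 lists an ongoing study of it in lupus membranous nephropathy.

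**Conclusion.** The inconsistency is real and should be resolved, either by carrying out the derivation or by recording why it was dropped. What the plan lacks is numerical QTcF data on longer exposure in this trial. The rationale rests on GS-9876; Protocol 1.2.2 and 1.5 report no relevant cardiovascular effect for filgotinib. The estimates would be within-group changes from the screening ECG, with a 90% half-width of about 4 to 8 ms under the assumed SD of 10 to 20 ms and n of 18 to 20. They would be less precise if fewer subjects enter the extension.

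**What to change.** Add to SAP 7.5:
- Derivation of QTcF from the recorded QT and RR (QT divided by the cube root of RR in seconds).
- An eight-number summary of QTcF and of its change from the screening (baseline) ECG, by treatment group, at Weeks 24, 36 and 48. Use the active-treatment grouping for re-randomised placebo subjects, so that their shorter time on active drug is visible.
- A count and a listing of subjects by prespecified categories of QTcF value and of increase from baseline, for reporting only.
- A statement that these are within-group changes with no scheduled on-treatment placebo ECG.

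If this is not done, record the omission and its reason in SAP 7.7.

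The cost is one derived variable and one or two tables, with no new assessments, provided that the eCRF holds the QT and RR values. Confirm that first.
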